II. Sodium oxybate modulates abnormally increased activation in SD and SD/VT patients. Using a sparse-sampling BOLD fMRI design and symptomatic speech production, we examine the effects of sodium oxybate on brain activation abnormalities in 3 SD and SD/VT patients to evaluate the mechanisms of central action of this novel pharmacological agent. Compared to healthy controls, before treatment, all patients exhibited typically increased brain activation during symptomatic speech production ($p \leq 0.05$, corrected) (Fig. 3-I) similar to abnormalities described before (Haslinger et al., 2005; Ali et al., 2006; [name] and Ludlow, 2010) and in our 1.2.2 *Preliminary Studies* above. After treatment, patients' brain activation was significantly attenuated and followed a nearly normal pattern present during normal speech production, with only few regions remaining hyperactive ($p \leq 0.05$, corrected) (Fig. 3-II). A two-tailed paired *t*-test calculation using the measure of the total number of significantly active brain voxels before and after treatment in patients showed that the drug-induced attenuation of abnormal functional activation was in average 49% ($p = 0.017$) (Fig. 3-III). Specifically, sodium oxybate treatment significantly decreased and normalized abnormally elevated brain activity in the prefrontal, premotor and auditory cortices as well as in the basal ganglia, thalamus, and cerebellum. In 1.2.2 *Preliminary Studies* presented above, we found these regions to have a greater extent of abnormal activation in SD/VT patients compared to SD patients.

[figure not shown]

Figure 3 depicts differences in brain activation in SD and SD/VT compared to healthy controls before (I) and after (II) treatment with sodium oxybate (voxelwise $p \leq 0.05$, corrected). Panel (III) shows significantly decreased number of hyperactive brain voxels after the treatment compared to the before treatment baseline in patients ($p = 0.017$).

Collectively, our preliminary data indicate that sodium oxybate is effective in SD patients and especially in those who present with a VT component. Furthermore, our data suggest that the effects of sodium oxybate treatment are exerted through the modulation of overly increased brain activation.

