Study population and Sample size. To our knowledge the central effects of sodium oxybate has not been reported. Therefore, to estimate the number of patients to be included in this study, we reviewed our pilot fMRI study in SD and SD/VT patients. Compared to baseline, we found an average of 49% reduction of overly increased brain activation after treatment with sodium oxybate. Power analysis determined a sample size of 22 patients in each group to have 80% power at 0.025 to detect changes in brain activation when comparing before and after treatment conditions. We propose to recruit 25 ethanol-responsive SD and SD/VT subjects per group to account for the subjects' dropout possibilities and to increase statistical power.

2.3.2 Study #2: Evaluation of combined central effects of sodium oxybate and botulinum toxin treatments in patients with SD and SD/VT using fMRI during symptomatic speech production. In this study, we will use the same fMRI design as used in the Similar to *Studies 1.3.1* and *2.3.1* to examine the combined effects of sodium oxybate and botulinum toxin on brain activation changes due to the treatment.

We estimate that about 40% of all recruited patients (mostly with ADSD) will report some benefits from botulinum toxin injections. These patients will be enrolled in this study and will undergo the third scanning session after receiving their botulinum toxin treatment. They will be asked to take their individualized dose of sodium oxybate T.I.D. after the completion of the *Study 2.3.1* and until the end of this study. We predict that about 60% of SD (typically ABSD) and SD/VT patients recruited to the *Study 2.3.1* will report limited, if any, benefits from botulinum toxin treatment. These patients will, therefore, be replaced with newly recruited patients, whose symptoms do response to both alcohol intake and botulinum toxin treatment. Thus, at the time of this study, all patients will be treated with both sodium oxybate and botulinum toxin injections. The decision of whether sodium oxybate should be continued after the completion of all studies in this proposal will be made by the patient and his/her referring physician.

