Because more than 50% of patients experience breathiness with mean duration of 10.3 days and 14% of patients develop dysphagia to liquids with mean duration of 2 days as most common side effects following botulinum toxin injections (Novakovic et al., 2011), we will acquire the fMRI data at least 14 days after the botulinum toxin treatment.

We will use the same *fMRI design* as in the *Studies 1.3.1* and *2.3.1*. *Data analysis* will follow the same pipeline as described in *Study 2.3.1*. The power for this study is the same as in *Study 2.3.1*.

2.4 Expected Outcomes. Upon the successful completion of the studies in Specific Aim #2, we expect to have determined the brain mechanisms of action of a novel pharmacological agent, sodium oxybate, as a potentially alternative treatment for symptom management in SD and SD/VT patients. Furthermore, we expect to identify the extent of central effects from the combined use of sodium oxybate and botulinum toxin. This treatment strategy may be useful in prolongation of the effects of botulinum toxin injections in those patients who receive limited benefits, mainly due to presence of the VT component. Collectively, we expect that outcome of the proposed studies will establish a strong scientific basis for the use of newly developed treatment strategies in SD and SD/VT patients.

2.5 Potential Problems and Alternative Strategies. Similar to the studies under Specific Aim #1, a potential problem may arise from an insufficient availability of patients who must be symptomatic and ethanol-responsive. However, such a problem seems unlikely for reasons described under subsection 1.5.

A different strategy for the evaluation of central effects of sodium oxybate might be the initial conduct of large-scale clinical trials using this drug in SD and VT and then exploration of its central mechanism of action in these patients. We, however, decided against this strategy because the establishment of a scientific basis for the use of sodium oxybate in SD and VT patients is of a more importance than the empirical test of yet another medication in these patients. Furthermore, the conduct of a large-scale clinical trial from the statistical point of view may be difficult as the recruitment of large numbers of eligible patients with these rare disorders may present a significant challenge.

Timetable

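### Study 2.3.2 takes over the 80% power of Study 2.3.1, but the plan names no contrast or effect for it and its enrolment rule and headcount do not jointly support that figure

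*Combined protocol and SAP*

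**What the plan says.** Section 2.3.1 (Study population and Sample size) starts from the pilot: "we found an average of 49% reduction of overly increased brain activation after treatment with sodium oxybate". It continues: "Power analysis determined a sample size of 22 patients in each group to have 80% power at 0.025 to detect changes in brain activation", and the comparison is specified as "when comparing before and after treatment conditions". Recruitment is set at 25 per group.

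Section 2.3.2 then adds a scan after botulinum toxin in patients who are also taking oxybate. On who enters it: "We estimate that about 40% of all recruited patients (mostly with ADSD) will report some benefits from botulinum toxin injections". Those patients have a third scan. The other 60% or so do not continue: "These patients will, therefore, be replaced with newly recruited patients, whose symptoms do response to both alcohol intake and botulinum toxin treatment". The analysis is to follow the Study 2.3.1 pipeline, and on sample size the only statement is "The power for this study is the same as in" Study 2.3.1.

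Protection of Human Subjects, section 1a, gives a different schedule. In each group, 12 patients from Aim 1 complete the oxybate scan and the combined scan, with the Aim 1 scan as baseline. The other 13 complete baseline, oxybate and combined scans. Total recruitment is 86.

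**The concern.** A power figure belongs to a particular contrast, effect, variance and number of analysable patients. Study 2.3.1 has a stated contrast and a stated n. Study 2.3.2 has neither, and its conditions differ. Its patients are restricted to those who benefit from toxin. They take oxybate three times daily rather than as one office dose, and they are scanned at least 14 days after an injection. Nothing in the plan shows that the Study 2.3.1 effect or variance carries over.

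The number of usable pairs is also unsettled. Replacing patients keeps the headcount, but a within-patient comparison needs an earlier scan from the same patient, and section 2.3.2 does not say that replacements have one.

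Section 2.4 expects to identify the extent of the combined effects. With 80% attached, a null result could be taken as good evidence that the combination does little. The plan as written gives no basis for that reading.

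**Working it through.** **1. Can the Study 2.3.1 figure be reproduced?** No. Section 2.3.1 gives a 49% mean reduction and no standard deviation. The only other input is the two-tailed paired p = 0.017 in section 2.2.2, from a pilot described as covering "brain activation abnormalities in 3 SD and SD/VT patients", which may mean 3 in all or 3 of each type. Using dz = t/√n:

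- n = 3: t = 7.57, dz = 7.57/√3 = 4.37; 80% power needs 3 to 4 pairs (one- or two-sided).
- n = 6: t = 3.52, dz = 3.52/√6 = 1.44; 80% power needs 6 to 8 pairs.

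Neither gives 22.

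**2. What effect does 22 per group imply?** For a paired t-test, power = P(T > t_crit), where T is noncentral t with n − 1 degrees of freedom and noncentrality dz·√n. Solving for 80% at n = 22:

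- two-sided 0.025: dz = 0.70, so the SD of the percentage change would be 49/0.70 = about 70 points;
- one-sided 0.025: dz = 0.63, SD about 78 points.

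The plan states neither dz nor sidedness for this calculation. All power values below are conditional on this back-solved effect.

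**3. How many pairs does the plan provide?**

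| Source | Patients per group in the combined scan | Earlier scans |
|---|---|---|
| Section 2.3.2 | 0.40 × 25 = 10 carried over (if evenly spread), plus 0.60 × 25 = 15 replacements | Described for the 10 only |
| Human subjects section 1a | 12 + 13 = 25 | All have baseline and oxybate scans |

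The total of 86 is 60 (Aim 1) + 26 (new for Aim 2). Replacing 60% of 50 patients adds about 30, giving 86 + 30 = 116. Applying the section 2.3.2 rule within a total of 86 therefore leaves about 10 per group, against the 22 that the plan says 80% power requires.

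**4. Power if the effect equals the implied Study 2.3.1 effect**

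| Pairs per group | Two-sided (dz 0.70) | One-sided (dz 0.63) |
|---|---|---|
| 25 | 86% | 85% |
| 22 | 80% | 80% |
| 10 | 37% | 42% |

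With 10 pairs, 80% power (two-sided) needs dz of about 1.14.

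If the 15 replacements have no earlier scan, and their combined scans are pooled with the earlier scans of the 15 patients they replace, an inverse-variance combination with the 10 pairs gives about 82%, 75% or 66% two-sided. These correspond to assumed within-patient correlations of 0.3, 0.5 and 0.7. The plan does not describe such an analysis.

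**5. Power if the contrast is combined treatment versus oxybate alone.** The plan gives no size for this increment. Assuming 25%, 50% or 75% of dz 0.70, 25 complete pairs give 8%, 28% or 60% (two-sided).

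**The case against.** The strongest defence is the human subjects schedule. If all 25 per group complete every scan and the combined effect is at least that of oxybate alone, power is about 86%, above the stated 80%. That stands as arithmetic. It does not rescue the sentence, because the schedule conflicts with the replacement rule in section 2.3.2 and leaves no room for replacements in the total of 86.

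A second defence is that replacement keeps each group at 25, and that reusing the Study 2.3.1 pipeline, which compares each patient with his or her own pre-treatment scan, suggests replacements would have a baseline. That is plausible. The plan is silent on their earlier scans; it does not rule them out. Ten pairs is therefore one reading of the plan and not its declared sample.

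Third, the comparator may be pre-treatment baseline, for which the combined effect could equal or exceed that of oxybate alone. This also stands. The increment over oxybate is only one possible contrast, and the percentages in step 5 apply to that one alone.

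Fourth, dz 0.70 is inferred from an n that the pilot does not reproduce. At the pilot-based dz of 1.44, ten pairs would give about 95%. A pilot of 3 or 6 patients is a weak basis for planning, but the point confirms that 37% is conditional.

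A reader might infer that Study 2.3.2 cannot reach 80%, or that almost no SD/VT patients would supply pairs. The documents support neither. The first fails under the 25-pair schedule. The second would require combining the toxin response rates in section 2.1 with the looser criterion of some benefit in section 2.3.2, and would ignore replacement.

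**Conclusion.** The equal-power statement is unsupported and should not stand. This rests on the text alone: no contrast, effect or standard deviation is given for the combined treatment, and the section 2.3.2 enrolment rule and the human subjects headcount cannot both hold.

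The size depends on how those gaps are filled. At the implied dz of 0.70, two-sided power runs from 86% (25 complete pairs, same effect) to 37% (10 pairs, same effect), and to 28% if all 25 pairs are available but the effect is half as large. The even spread of the 40% across groups, the back-solved dz and the effect fractions are assumptions. The finding is a missing justification together with an internal inconsistency. It does not show that the study is underpowered under every reading.

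**What to change.** 1. Delete the equal-power sentence from section 2.3.2.
2. Reconcile section 2.3.2 with section 1a of Protection of Human Subjects: whether patients are replaced, which scans replacements receive, and whether the total remains 86 or rises by about 30.
3. Name the contrast: combined treatment versus pre-treatment baseline, or versus oxybate alone.
4. State the number of patients per group with both scans for that contrast, and the power or detectable dz at that number, with sidedness and the assumed effect and standard deviation. With 10 pairs, the detectable dz at 80% power (two-sided 0.025) is about 1.14.
5. Report Study 2.3.2 as estimation with confidence intervals, so that a null result is not read as coming from a study with 80% power.

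The cost is wording and probably a less favourable stated figure. These edits do not themselves require extra patients or scans. If the sponsor keeps the replacement rule, the additional recruits already follow from section 2.3.2 and need to be counted.

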2.1 Introduction. Treatment options of SD and VT are limited and directed to short-term symptom management, usually employing medications such as botulinum toxin injections into the laryngeal muscles. However, botulinum toxin treatment is not beneficial in all SD patients. It is estimated that 90% of ADSD patients receive 90% benefit from botulinum toxin treatment, while only 10% of ABSD patients receive 70% benefits ([name], 2010). The benefits of botulinum toxin treatment are even much less, if any, for patients with VT or combined SD and VT. In addition, botulinum toxin treatment is burdensome both psychologically and financially because injections are relatively expensive and must be repeated every 3-4 months throughout a patient's life. Furthermore, the "gold standard" treatment of SD with botulinum toxin is based on an empirical rationale, as the mechanisms of action by which botulinum toxin relieves SD symptoms remain unclear. Studies of central effects of botulinum toxin treatment in SD patients are limited and so far produced conflicting results. An fMRI study found no effects of treatment on cortical activation but decreased subcortical activation within the thalamus and basal ganglia during vowel production in ADSD patients (Haslinger et al., 2005). Another study, using PET during narrative speech production in ADSD patients, found decreased activation in the motor cortex, cerebellum, thalamus and basal ganglia and increased activation in the sensory association areas, operculum and midbrain after treatment with botulinum toxin (Ali et al., 2006).

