2.3 Research Design

The following 2 groups of patients will participate in the proposed studies of Specific Aim #2: (1) SD patients, and (2) SD/VT patients. Because sodium oxybate has been shown to be effective in patients with movement disorders who self-report symptom improvement after alcohol intake, only ethanol-responsive patients will be recruited for the purposes of these studies. We estimate that 60% of ethanol-responsive patients per group, who participated in the studies in Specific Aim #1, will also participate in the studies in Specific Aim #2. Both ADSD and ABSD patients will be included and closely matched with ADSD/VT and ABSD/VT patients. Patients will be identified according to the screening and detailed examinations as described in Specific Aim #1. In this Specific Aim, we will (1) evaluate the central effects of sodium oxybate in SD and SD/VT patients to determine the relationship between improved clinical symptoms and modulated brain function, and (2) examine the extent of central effects from the combined use of sodium oxybate and botulinum toxin treatments as an alternative treatment schedule for patients with limited benefits.

2.3.1 Study #1: Mapping central effects of sodium oxybate treatment in patients with SD and SD/VT using fMRI during symptomatic speech production. Similar to the fMRI study under Specific Aim #1, we will use a sparse-

sampling event-related BOLD fMRI design during symptomatic voice and speech production on a 3.0 Tesla Philips MRI scanner. Each patient will participate in 2 fMRI sessions, before and after treatment with sodium oxybate. All recruited patients will have to be symptomatic; if they are treated with botulinum toxin injections, they may be included only if they are symptomatic at the end of their botulinum toxin treatment cycle. During each scanning session, the patient will be asked to perform short English sentences as well as repetitive and continuous vowel /i/, designed to elicit SD and VT symptoms. Four scanning sessions will be acquired with a total of 36 experimental trials and 24 baseline resting conditions. Structural MRI will be acquired for an anatomical reference.

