Following the initial (baseline) fMRI session, patients will receive an individualized tolerable and efficacious single dose of sodium oxybate, given orally in the office. Patients' symptoms will be evaluated and videotaped one hour after receiving this dose with the immediately followed-up second fMRI session, during which the patients will be asked to produce the same tasks performed during the pre-treatment fMRI study. Patients' post-treatment scans will be compared to their pre-treatment scans to identify differences in brain activation abnormalities due to the effects of sodium oxybate treatment. Voice and speech production during both scanning sessions will be digitally recorded for acoustical analysis and correlations with the central effects of the treatment.

Data analysis. Using AFNI software, fMRI data analysis will include initial pre-processing followed by analysis of the task-related responses using multiple linear regression with a single regressor for each task convolved with a canonical hemodynamic response function, as described above in *1.3.1 Study of Specific Aim #1*. For group analysis, a two-way ANOVA will be conducted with subject as a random factor and task as fixed factor (corrected $p \leq 0.025$). Conjunction analysis at a cluster significance threshold of $p < 0.005$ will determine common and distinct regions of activation within the patient group during task production in the pre- and post-treatment fMRI sessions. Finally, pre- and post-treatment neuroimaging findings will be correlated with the behavioral data derived from acoustical analysis of voice and speech recordings.

Additionally, to determine the extent of sodium oxybate effects on speech network dynamics, we will re-examine functional and effective network connectivity using the same PPI and DCM procedures as described in the *Study 1.3.1*.

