a. **Human Subjects Involvement, Characteristics, and Design.** As described in the *Approach* section, we will recruit SD, SD/VT and healthy control subjects for participation in the proposed studies. Both ADSD and ABSD patients as well as ADSD/VT and ABSD/VT patients will be included and matched with each other in their age, gender and SD type (AD or AB). Clinically healthy subjects will be those who do not have present or past history of any neurological, psychiatric or laryngological problems. Controls will be carefully matched with SD and SD/VT populations by their age, gender, and ethnicity.

For all studies in Specific Aim #1, we propose to recruit the same 20 subjects per SD, SD/VT and control groups. Because the majority of VT patients report improvement of their voice symptoms after alcohol intake, we predict that at least 60% (12 patients) of recruited SD/VT group will also be ethanol-responsive. To assure homogeneity between patient populations, we will carefully match SD and SD/VT patients according to their report of alcohol effects, in addition to their age, gender and an SD type match. A total of 60 subjects will undergo 2-hour scanning session for the studies in Specific Aim #1.

For all studies in Specific Aim #2, we will recruit 25 ethanol-responsive SD and SD/VT patients. We estimate that 12 ethanol-responsive patients per group, who participated in the studies in Specific Aim #1, will also participate in the studies in Specific Aim #2. Thus, this will require us to recruit additional 13 SD and 13 SD/VT patients for the proposed studies in Specific Aim #2. A total of newly recruited patients will be 26. The patients will participate in the fMRI studies of this Specific Aim according to the following schedule:

- (1) Because the 12 patients/group, who already underwent neuroimaging studies in Specific Aim #1, will not need a pre-treatment baseline scanning session, they will only complete two 2-hour post-treatment scans with sodium oxybate and botulinum toxin + sodium oxybate, respectively;
- (2) the remaining 13 patients/group will complete three 2-hour scanning sessions, which will include one pre-treatment baseline scan and two post-treatment scans with sodium oxybate and botulinum toxin + sodium oxybate, respectively.

A total number of subjects recruited for studies under both Specific Aims will be 86.

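### An estimated 12 of 25 Aim 2 patients per group reuse their Aim 1 scan as the pre-treatment baseline with no limit on its age, and the written Aim 2 ANOVA has no pre/post factor.

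*Combined protocol and SAP*

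**What the plan says.** **Who is rescanned.** Protection of Human Subjects, section 1a, gives the overlap between the aims as an estimate: "We estimate that 12 ethanol-responsive patients per group, who participated in the studies in Specific Aim #1" are expected to continue into Aim 2. The rule for them follows: "Because the 12 patients/group, who already underwent neuroimaging studies in Specific Aim #1, will not need a pre-treatment baseline scanning session". They have two post-treatment scans, one on sodium oxybate and one on sodium oxybate plus botulinum toxin. The remaining 13 per group have a new baseline and the same two post-treatment scans.

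**What is timed.** In section 2.3.1 patients are "evaluated and videotaped one hour after receiving this dose with the immediately followed-up second fMRI session". For the combined-treatment scan, section 2.3.2 sets only a minimum: "we will acquire the fMRI data at least 14 days after the botulinum toxin treatment". For the baseline, section 2.3.1 gives only the order, with the dose coming after the baseline session. Section 1a adds that scans follow the treatment schedule. The Timetable runs both aims in parallel through the funding period.

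**How the baseline is used.** Section 2.3.1 says "Each patient will participate in 2 fMRI sessions, before and after treatment with sodium oxybate" and compares each patient's post-treatment scans with the pre-treatment scans "to identify differences in brain activation abnormalities due to the effects of sodium oxybate treatment". The group model reads "a two-way ANOVA will be conducted with subject as a random factor and task as fixed factor". A conjunction analysis of the two sessions and correlations with acoustic measures follow. Study 2.3.2 uses the same pipeline.

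**The concern.** The within-group pre/post change is the plan's measure of the drug's central effect. For nearly half of each group the pre value comes from a scan made for another aim, and its distance from the dosing visit is not limited. A change with a consistent direction over that interval would be counted as drug effect, or would hide one, depending on its sign.

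Elapsed time could matter on the plan's own account. Section 2.1 says that toxin injections "must be repeated every 3-4 months", so a reused scan older than about one cycle could have a further injection between pre and post. The same section cites studies, with conflicting results, in which toxin altered brain activation.

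The analysis as written could not reveal such a problem. A model with only subject and task has no term for pre versus post, and none for where the baseline came from.

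**Working it through.** **1. The plan's own counts.** Inputs are 20 per group in Aim 1, a 60% carry-over (sections 2.3 and 1a), and 25 per group in Aim 2 (section 2.3.1, sample size).

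- Carried over: 0.60 x 20 = 12 per group.
- New: 25 - 12 = 13 per group, and 2 x 13 = 26 in all.
- Total: 3 x 20 + 26 = 86.

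All four agree with section 1a.

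**2. Is the Aim 1 scan the baseline?** Section 1a does not say so outright. However, section 2.3.1 compares post with pre in each patient, and the 12 have no other pre-treatment scan. No other reading fits.

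**3. Share of reused baselines.** As planned, 12/25 = 0.48. If 22 remain (the calculated sample size), the share lies between 9/22 = 0.41 and 12/22 = 0.55, depending on which patients are lost. If only the roughly 40% with toxin benefit (section 2.3.2) could drift, and that figure is assumed to apply to the 12, then 0.40 x 12 = 4.8 and 4.8/25 = 0.19.

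**4. Bias.** Let d be the mean true change and D the mean drift in the reused scans. The expected group change is (13 d + 12 (d + D))/25 = d + 0.48 D. The documents give neither the size nor the sign of D, so the values below are assumptions, in SD of the change and in either direction.

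| D | Bias, share 0.19 | Bias, share 0.41 | Bias, share 0.48 | Bias, share 0.55 |
|---|---|---|---|---|
| 0.2 | 0.04 | 0.08 | 0.10 | 0.11 |
| 0.3 | 0.06 | 0.12 | 0.14 | 0.16 |
| 0.5 | 0.10 | 0.20 | 0.24 | 0.27 |

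**5. What that does to one test.** This simulates a single paired t-test with n = 25, two-sided 0.025 and no drug effect, 400,000 runs per case.

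| Drift | D = 0.2 | D = 0.3 | D = 0.5 |
|---|---|---|---|
| 12 patients, same direction | 3.9% | 5.8% | 12% |
| 5 patients, same direction | 2.8% | 3.0% | 3.8% |

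Drift with zero mean leaves the rate at about 2.5%. These are not error rates of the corrected voxelwise analysis.

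**6. The written model.** Section 1.3.1 names group as a factor because groups are to be compared. Section 2.3.1 intends a pre/post comparison but names only subject and task. The conjunction step maps regions common to, or distinct between, the sessions. It does not estimate a change with its error.

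**7. Could an interaction test rescue it?** Comparing the change in 12 reused with 13 new baselines has noncentrality D x sqrt(12 x 13/25) = 2.50 D. With 23 degrees of freedom and two-sided 0.025, power is about 4%, 6% and 14% for D = 0.2, 0.3 and 0.5. Such a test would rarely detect the drift in question.

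**The case against.** **The toxin route is largely controlled.** Sections 1.3 and 2.3.1 admit toxin-treated patients only when symptomatic at the end of their cycle. The exclusion criteria require them to be fully symptomatic on entry, except for Study 2.3.2. Section 1.5 describes eligibility as the last toxin at least 3 months earlier, and section 2.5 refers back to section 1.5 on patient availability. Pre and post scans are therefore meant to fall in the same phase of the cycle, and an intervening injection that has worn off need not shift the mean. Section 2.3.2 also expects about 60% of SD and SD/VT patients recruited to Study 2.3.1 to report limited toxin benefit, if any. This stands, and it makes a large toxin-driven drift less likely. It leaves elapsed time unbounded, because the rules are tied to recruitment or entry and a re-check before the post-dose scan is not spelled out.

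**A reader might infer that the reused scans will be old.** The documents do not support that. Aims run in parallel allow a short gap, the bars of the timetable cannot be read in the available text, and no interval is stated for the 13 new baselines either. Section 1.3 rejects older scans from a different scanner, but Aim 1 scans share the scanner and tasks of Aim 2.

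**A reader might see a contradiction** between two sessions for each patient in section 2.3.1 and no new baseline for 12 per group in section 1a. The two are compatible if the Aim 1 scan is the before session; the plan only needs to say so.

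**The missing session factor is a separate fault.** It would remain if all 25 had fresh baselines. That is true. It belongs here because it is also why the written model could not expose a problem with the reused scans.

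**Conclusion.** The point holds in a limited form. The plan lets an estimated 48% of each Aim 2 group use a baseline of unstated age, states no baseline-to-dose interval for any patient, and attributes the pre/post difference to sodium oxybate with a model that has no pre/post factor.

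The possible bias in the within-group change is about 0.48 D, or 0.19 D if only patients with toxin benefit drift. Whether D differs from zero, and in which direction, is unknown; every value of D used here is an assumption.

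Three stronger conclusions do not follow:

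- The trial's false-positive rate cannot be called inflated. The illustration covers one paired test with drift in one direction, and zero-mean drift does not raise the rate.
- No loss of power can be quantified, because the plan gives no SD of the change.
- The SD versus SD/VT comparison is not shown to be biased, since drift equal in both groups largely cancels.

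A common window would make baselines comparable, but in an uncontrolled pre/post design it would not separate drug from time or session effects.

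**What to change.** 1. Use the alcohol-response question at intake (section 1a, Appendix 1) to identify likely Aim 2 patients before their Aim 1 scan, and schedule that scan so that it is also their pre-dose baseline. State one baseline-to-dose window for all 25 per group. The investigator should set its length to fit the process of individualising the dose.
2. In section 2.3.1, write session (pre/post) as a within-subject factor in the Aim 2 model, and carry it into Study 2.3.2, which uses the same pipeline.
3. Record the baseline-to-dose interval for every patient, and report its median and range by group and baseline source. Report the new-baseline patients as a descriptive sensitivity analysis. Do not rely on a 12 versus 13 interaction test.
4. State in section 2.3.1 that the Aim 1 scan is the before session for carried-over patients, so that it agrees with section 1a. Word the conclusion as pre/post change.

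The cost is less flexible scheduling for about 12 patients per group, and some Aim 1 scans may have to wait until the dosing visit is arranged. No extra scans are needed. The window need not mean the same day, which would put two sessions of up to 2 hours together when the human-subjects section is already concerned to avoid exhaustion during scanning.
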